### 1.4 Study intervention

In accordance with the 2019 AHA/ASA guidelines for early management of AIS and recommendations from the steering committee (SC): In EVT alone group, EVT will be performed as quickly as possible. In IVT followed by EVT group, patients will receive IVT with alteplase (0.9 mg/kg, maximum 90 mg in one hour) before EVT. Efforts will be made to minimize delays in EVT initiation due to IVT administration. EVT techniques include retrievable stent thrombectomy, thrombus aspiration, balloon angioplasty, stent implantation, or combinations thereof. The specific EVT approach will be at the discretion of the treatment team.

### 1.5 Sample size

Currently, no large-scale randomized controlled trials (RCTs) exist in this field. Therefore, the calculation of the sample size for this study will be based on the results of the RESCUE-RE registry study conducted in the Chinese population. According to the study, the proportion of patients achieving a mRS score  $\leq 2$  at 90 days post-procedure was 42.03% in the IVT followed by EVT group and 26.14% in the EVT alone group.

Based on the superiority hypothesis, the study aims to determine whether the proportion of patients achieving a modified Rankin Scale (mRS) score of  $\leq 2$  at 90 days is higher in the IVT followed by EVT group compared to the EVT alone group. The statistical hypotheses are defined as follows:

Null Hypothesis  $H_0: p_T - p_C \leq 0$

Alternative Hypothesis  $H_1: p_T - p_C > 0$

$\alpha = 0.025$  (per side),

Assuming a one-sided type I error rate of 0.025 and a statistical power of 80%, with equal allocation between the two groups (1:1), each group will require 136 patients (a total of 272 patients). Considering an anticipated dropout rate of approximately 20%, the final sample size will be adjusted to 340 patients, with 170 patients per group.

Given limited reference data and evidence suggesting the non-inferiority of EVT alone in the anterior circulation, an interim analysis will be conducted after one-third (114) of patients have completed follow-up for the primary endpoint. At this stage, the Data and Safety Monitoring Board (DSMB) will perform a sample size re-estimation based on the efficacy data obtained from both groups.

If the interim analysis the efficacy of the two groups is found to be similar, the study hypothesis will be adjusted to a non-inferiority hypothesis, aiming to verify whether EVT alone is non-inferior to IVT followed by EVT. The specific statistic hypotheses are as follows:

Null Hypothesis  $H_0: p_T - p_C \leq -\Delta$

Alternative Hypothesis  $H_1: p_T - p_C > -\Delta$

$\alpha = 0.025$  (per side),

In this context,  $p_T$  represents the proportion of patients in the IVT followed by EVT group achieving a 90-day mRS score of  $\leq 2$ , while  $p_C$  represents the proportion in the EVT alone group.  $\Delta$  denotes the non-inferiority margin, defined as a positive value. Assuming that the efficacy of the two groups is equivalent, with both achieving a 90-day mRS score of  $\leq 2$  in 42.03% of patients, and under the conditions of a one-sided type I error rate of 0.025 and a non-inferiority margin of -15%, the current sample size of 170 patients per group provides 80% power to detect non-inferiority.

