10.4 Interim analysis

An interim analysis will be conducted after one-third (114) of the patients have completed follow-up for the primary endpoint, with the primary objective of reassessing the sample size. The DSMB will calculate the conditional power based on the available data and provide recommendations to the research team regarding any potential adjustments to the sample size. If the efficacy advantage of the IVT followed by EVT group over the EVT alone group is less than anticipated, the sample size may be expanded appropriately, with an upper limit of no more than 20% of the original sample size. If the efficacy of the two groups appears to be similar, the study design will shift to a non-inferiority framework, evaluating whether EVT alone is non-inferior to IVT followed by EVT.

The study does not include predefined conditions for early termination, except in cases where the DSMB recommends stopping the trial for safety reasons. Otherwise, enrollment will continue until the target sample size is achieved.

11. Quality control and quality assurance

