## 3.4 Interim Analysis

An interim analysis is planned once 1/3 (114 subjects) of the total population has completed the follow-up for the primary endpoint. During this interim analysis, the DSMB will conduct a sample size re-estimation based on the efficacy data obtained from both groups.

If the efficacy advantage of the IVT followed by EVT group over the EVT alone group is less than anticipated, the sample size will be appropriately increased. The DSMB will calculate the **conditional power** from the current data and provide recommendations to the BEST-BAO research team regarding sample size adjustments or modifications to the study hypothesis. The maximum increase in sample size will not exceed 20% of the original planned sample size.

If the efficacy of the two groups is found to be similar, the study hypothesis will be adjusted to a **non-inferiority hypothesis** to determine whether EVT alone is non-inferior to IVT followed by EVT. Assuming both groups achieve similar efficacy, with 42.03% of patients achieving a 90-day mRS  $\leq 2$ , and with a one-sided type I error rate of 0.025 and a non-inferiority margin of -15%, the current sample size of 170 patients per group will provide 80% power to demonstrate non-inferiority.

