#### 3.9.1 Primary efficacy endpoint

The primary efficacy endpoint, "the proportion of patients with mRS  $\leq 2$  at 90 days after onset," will be statistically described by treatment group. The 95% confidence intervals (CIs) will be calculated using the exact Clopper-Pearson method. Additionally, a bar chart will be used to display the distribution of mRS scores.

When using a superiority hypothesis test, the specific statistical hypotheses are as follows:

Null hypothesis  $H_0: p_T - p_C \leq 0$

Alternative hypothesis  $H_1: p_T - p_C > 0$

$\alpha = 0.025$  (one side)

If the hypothesis is adjusted to a non-inferiority hypothesis after the interim analysis, the specific statistical hypotheses are as follows:

Null hypothesis  $H_0: p_T - p_C \leq -15\%$

Alternative hypothesis  $H_1: p_T - p_C > -15\%$

$\alpha = 0.025$  (one side)

Here,  $p_T$  represent the proportions of patients with mRS  $\leq 2$  in the IVT followed by EVT and EVT alone groups, respectively.

A log-binomial model will be used, assuming the primary endpoint follows a binomial distribution. A log-link function will be applied, with covariates including age, pre-stroke mRS, time from onset to randomization, stroke severity (NIHSS score), and collateral circulation. Adjusted and unadjusted risk difference (RD) and risk ratio (RR) with their 95% confidence intervals will be reported.

For superiority, if the lower bound of the 95% CI of the adjusted RD  $> 0$ , superiority is established.

For non-inferiority, if the lower bound of the 95% CI of the adjusted RD  $> -15\%$ , non-inferiority is established.

Additionally, Chi-square tests (expected cell count  $\geq 5$ ), continuity-corrected chi-square tests (1 expected cell count between 1 and 5), or Fisher's exact test ( $\geq 1$  expected cell count  $< 5$  or any expected cell count  $< 1$ ) will also be used for group comparisons, and P-values will be reported.

The mRS score used in the primary analysis will be based on centralized assessments. If centralized assessments are missing for certain subjects, local investigator assessments will be used by default. Sensitivity analyses will also use local assessments to evaluate the robustness of the results.

A list of all primary efficacy endpoint data for all visits (m-ITT, AT, PPS sets) will be provided.

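### The SAP's non-inferiority hypothesis and decision rule run in the wrong direction: they test IVT followed by EVT against EVT alone, and become easier to pass as EVT alone gets worse

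*SAP*

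**What the plan says.** The trial starts as a superiority trial of IVT followed by EVT over EVT alone. SAP 3.4 then provides: "If the efficacy of the two groups is found to be similar, the study hypothesis will be adjusted to a" non-inferiority hypothesis. SAP 1.5 gives the purpose of that hypothesis as "aiming to verify whether EVT alone is non-inferior to IVT followed by EVT", and Protocol 10.4 agrees: "evaluating whether EVT alone is non-inferior to IVT followed by EVT". In words, EVT alone is the arm under test and IVT followed by EVT is the reference.

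The formulas that follow in SAP 1.5 are `H0: p_T - p_C <= -Delta` against `H1: p_T - p_C > -Delta`, with Delta positive and the margin set at 15 points. Directly afterwards, SAP 1.5 says that p_T "represents the proportion of patients in the IVT followed by EVT group achieving a 90-day mRS score of" 2 or less, and that p_C "represents the proportion in the EVT alone group".

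SAP 3.9.1 repeats the hypotheses with −15% in place of −Delta and lists the arms in the same order: "in the IVT followed by EVT and EVT alone groups, respectively". It then gives two decision rules on one quantity:

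- "For superiority, if the lower bound of the 95% CI of the adjusted RD" is above 0, superiority is established.
- "For non-inferiority, if the lower bound of the 95% CI of the adjusted RD" is above −15%, non-inferiority is established.

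**The concern.** The words and the formulas ask opposite questions. With p_T as IVT followed by EVT, the alternative `p_T - p_C > -15%` says that IVT followed by EVT is not more than 15 points worse than EVT alone. That is non-inferiority of the arm meant to be the reference.

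After a switch this is the only primary decision rule in the plan. An analyst would hold a stated aim and a formula that cannot both be followed. Followed literally, the rule is met more readily the better IVT followed by EVT performs, so data against EVT alone would be reported as establishing its non-inferiority. If the analyst notices and follows the words instead, the direction of the primary test is chosen at the analysis stage, which pre-specification is meant to prevent.

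**Working it through.** **Step 1. Direction of RD.** SAP 3.9.1 does not say which arm is subtracted from which. The superiority aim is that IVT followed by EVT does better, and superiority is claimed when the lower bound of the adjusted RD is above 0. So RD = p(IVT+EVT) − p(EVT alone). This agrees with the definitions of p_T and p_C in SAP 1.5. The non-inferiority rule uses the same RD. Reading RD the other way round would repair that rule and break the superiority rule.

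**Step 2. The plan's own figure.** Inputs from SAP 1.5: 42.03% in both arms, margin 15 points, one-sided alpha 0.025, power 80%.

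- n per arm = 2 × 0.4203 × 0.5797 × (1.96 + 0.8416)² / 0.15² ≈ 170.
- Power at 170 per arm = Φ(0.15/SE − 1.96), with SE = √(2 × 0.4203 × 0.5797/170) = 0.0535, which gives 80.0%.

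The stated figure is reproduced. It cannot reveal the reversal, because with equal rates both directions give the same power.

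**Step 3. Two worked results** (unadjusted Wald interval, unpooled SE, 170 per arm).

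- 71/170 (41.8%) with IVT followed by EVT and 54/170 (31.8%) with EVT alone: RD = +10.0 points, SE = 5.2, 95% CI −0.2 to +20.2. Written rule: −0.2 > −15, passes. Rule for the stated aim: the lower bound of EVT alone minus IVT+EVT is −20.2, fails.
- 71/170 and 46/170 (27.1%): RD = +14.7 points, 95% CI +4.7 to +24.7. IVT followed by EVT is superior, and the written non-inferiority rule also passes. This is general: any lower bound above 0 is also above −15%.

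**Step 4. Pass probability of each rule taken alone.** IVT followed by EVT is held at 42.03%, and SE is computed from the two true rates:

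- written rule: Φ((p_IVT+EVT − p_EVT + 0.15)/SE − 1.96)
- rule for the stated aim: Φ((p_EVT − p_IVT+EVT + 0.15)/SE − 1.96)

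| True position of EVT alone | Written, 170 per arm | Stated aim, 170 per arm | Written, 136 per arm | Stated aim, 136 per arm |
|---|---|---|---|---|
| 15 points better | 2.5% | >99.9% | 2.5% | 99.9% |
| equal | 80.0% | 80.0% | 70.7% | 70.7% |
| 5 points worse | 96.5% | 47.1% | 92.2% | 39.3% |
| 10 points worse | 99.8% | 15.9% | 99.0% | 13.5% |
| 15 points worse | >99.9% | 2.5% | >99.9% | 2.5% |

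The 136 columns allow for the plan's 20% dropout. The bottom row is the null boundary of the stated aim, where the error rate should be 2.5%.

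**Step 5. Allowing for the switch.** The rule applies only if the interim analysis finds similar efficacy, and the SAP gives no criterion for that. I assume a switch when the observed interim difference is within 3, 5 or 10 points. Simulation: 2,000,000 trials per scenario, 57 per arm at interim, 170 per arm at the end including the interim patients, no sample size increase.

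| EVT alone truly worse by | Interim threshold | Switch occurs | Switch and pass, written | Switch and pass, stated aim |
|---|---|---|---|---|
| 15 points | 3 | 5.7% | 5.7% | 0.65% |
| 15 points | 5 | 10.0% | 10.0% | 1.0% |
| 15 points | 10 | 26.8% | 26.8% | 1.9% |
| 10 points | 3 | 12.5% | 12.5% | 4.1% |
| 10 points | 5 | 21.0% | 21.0% | 6.6% |
| 10 points | 10 | 46.9% | 46.8% | 12.3% |

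Once a trial has switched, the written rule almost never fails in these scenarios. With EVT alone 15 points worse, the rule for the stated aim passes in 11.3%, 10.4% and 7.2% of switched trials.

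**The case against.** The best defence is that the intention is clear. The aim is worded consistently in SAP 1.5, SAP 3.4 and Protocol 10.4. Protocol 4.5 and 10.1 name EVT alone as the arm under test and give a signed margin of −15%, which 4.5 specifies as a rate difference. A negative margin for EVT alone fits only the difference EVT alone minus IVT followed by EVT. A careful analyst would probably notice the clash and follow the words, so the near-certain false claim in Step 4 is a worst case. The error also sits on a branch the trial may never enter, and the Step 5 probabilities depend on thresholds that I supplied.

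Much of this stands as a limit on scope. It does not remove the contradiction. No section restates the hypotheses or the RD rule in the right direction, nothing says that the words prevail over the formulas, and Protocol 10.2 refers the detailed analytical methods to the SAP.

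A faulty text extraction does not explain it either. The sentence in SAP 3.9.1 that defines the symbols lacks p_C in the text available, which may be an extraction loss. The definitions in SAP 1.5 are intact, however, and the arm order in 3.9.1 matches them.

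**Conclusion.** The concern holds. On the switched path, the SAP's primary hypothesis and decision rule test the non-inferiority of the wrong arm. This follows from the SAP's own definitions and from the RD it shares with the superiority rule, and it depends on no numerical assumption.

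Applied literally at 170 per arm, the rule passes more than 99.9% of the time when EVT alone is 15 points worse, against the intended 2.5%. With the switch included, that is 5.7% to 26.8% of all trials against 0.65% to 1.9%, on assumed thresholds of 3 to 10 points. The probabilities are approximate, because they use unadjusted Wald intervals whereas the SAP decides on a covariate-adjusted RD; the direction of the error does not depend on this. The superiority path, the 170 per group and the stated 80% power are unaffected. Because this is a primary decision rule, it must be corrected.

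**What to change.** Amend SAP 1.5 and 3.9.1 together:

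- Write the non-inferiority hypotheses with the arms named: `H0: p(EVT alone) - p(IVT followed by EVT) <= -15%` against `H1: p(EVT alone) - p(IVT followed by EVT) > -15%`.
- Declare non-inferiority if the lower bound of the two-sided 95% CI of the adjusted difference, EVT alone minus IVT followed by EVT, exceeds −15%. Equivalently, keep IVT followed by EVT minus EVT alone and require its upper bound to be below +15%.
- State the direction of RD for each rule. If p_T and p_C are kept anywhere, define both in 3.9.1.
- Leave the superiority rule as it is.

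The cost is SAP wording, with no change to sample size, data collection or the superiority analysis. Since the change reverses a primary hypothesis, make it as a dated amendment by people who have not seen outcomes by arm. The documents do not say whether the interim analysis has taken place, so the amendment should record that.

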## 1.6 Randomization and blinding

The randomization process will use a web-based randomization system. Patients can be randomized (Appendix 16) when AIS-BAO is confirmed by CTA, MRA, or DSA.

Before a patient is registered in the study database, assigned groups and treatment allocation will remain inaccessible, and patients cannot be excluded from the study after the allocation is revealed. Both patients and treating physicians will be aware of the assigned treatment group. However, trained investigators, who are blinded to assigned groups and treatment allocation, will record endpoint-related information using standardized forms and procedures, and details of the interviews. These trained evaluators will assess mRS outcomes and evaluate neuroimaging results in a blinded manner. Information related to assigned groups and treatment allocation will be maintained separately from the study database. The SC will not be informed of interim analysis results on the efficacy and safety. Independent trial statisticians will combine treatment allocation data with study database for reporting to the DSMB.

## 1.7 Planned analyses

One interim analysis (involving hypothesis testing adjustments and sample size re-estimation) and one final analysis are planned.

## 1.8 Visit schedule

Assessment/Step	Baseline	Treatment/ Intervention	Follow-up period 				
			18–24 hrs after procedure	24–72 hrs after procedure	5–7 days after stroke onset	30±7 days after stroke onset	90±14 days after stroke onset
Informed Consent	X						
Inclusion/Exclusion Criteria	X						
Randomization	X						
Demographics 	X						
Medical History	X						
Vital Signs 	X	X	X	X	X		
Clinical Lab Tests 	X			X	X		
CT/CTA or MRI/MRA or CT/DSA	X			X 			
CT/MRI (Head)					X		
mRS Score	X		X	X	X	X	X
NIHSS Score	X		X	X	X		
GCS Score	X		X	X	X		
IVT/EVT 		X					
Vascular Recanalization		X		X			
eTICI Score		X					
mAOL Score	X			X			

PC-ASPECTS Score	X			X			
PMI Score	X						
PC-CS Score	X						
BATMAN Score	X						
BI Score						X	X
EQ-5D-5L Score						X	X
Concomitant Medications	X	X	X	X	X	X	X
Death		X	X	X	X	X	X
ICH/sICH		X		X	X		
Procedure-Related Complications		X	X	X	X	X	X
New Territory Embolization		X					
New Infarction				X	X		
AE/SAE		X	X	X	X	X	X

**Abbreviations:** h, hours; CT, Computed tomography; CTA, Computed tomographic angiography; MRI, Magnetic resonance imaging; MRA, Magnetic resonance angiography; DSA, Digital subtraction angiography; mRS, Modified Rankin Scale; NIHSS, National Institutes of Health Stroke Scale; GCS, Glasgow Coma Scale; EVT, Endovascular treatment; IVT, Intravenous thrombolysis; eTICI, Extended thrombolysis in cerebral infarction score; mAOL, Modified arterial occlusion lesion score; PC-ASPECTS, Posterior circulation acute stroke prognosis early CT score; PMI, Pons-midbrain index; PC-CS, Posterior circulation collateral score; BATMAN, Basilar artery on CTA score; BI, Barthel index; EQ-5D-5L, EuroQoL five dimensions five levels health questionnaire; ICH, Intracranial hemorrhage; sICH, Symptomatic intracranial hemorrhage; AE, Adverse event; SAE, Serious adverse event.

**Notes:**

(1) Follow-Up: At  $30\pm 7$  days and  $90\pm 14$  days, follow-ups are conducted through telephone,

---

video calls, or in-person visits.

- (2) Demographics: Includes basic patient information such as sex, age, BMI, etc.
- (3) Vital Signs: Covers temperature, heart rate, respiratory rate, and blood pressure.
- (4) Clinical Laboratory Tests: Encompasses blood biochemistry, complete blood count, and coagulation parameters.
- (5) Imaging Follow-Up: Investigators are required to complete imaging evaluations at 24–72 hours after EVT procedure. If clinical deterioration necessitates earlier imaging, assessments can be conducted within 24 hours. In such cases, angiography (CTA or MRA) should be completed as synchronously as possible. In addition, given logistical constraints such as insurance policies and patient safety during transportation, the 24–72-hour imaging requirement for these cases can be waived.
- (6) IVT/EVT: Includes thrombolytic drug details (type, dose, timing, and route), time intervals from symptom onset to various procedural steps, and specifics of devices and sedation/anesthesia used during the procedure..

## 2. Evaluation criteria

### 2.1 Efficacy Endpoints

#### 2.1.1 Primary Endpoint

The primary endpoint of this trial is the proportion of patients achieving a mRS score  $\leq 2$  at 90 days after stroke onset. The mRS is the preferred parameter for assessing disability in stroke-related clinical trials. It is an ordinal scale with 7 levels, ranging from 0 to 6, where a score of 6 indicates death.

Assessments will be conducted by trained and independent investigators who are blinded to group assignments and the treatments received. These assessments will be based on standardized follow-up reports completed by blinded study personnel, through either outpatient visits or telephone interviews.

#### 2.1.2 Secondary endpoints

The secondary endpoints are as following:

- (1) Proportions of patients with mRS = 0 or 1 at 90 days after stroke onset.
- (2) Proportions of patients with mRS = 0–3 at 90 days after stroke onset.
- (3) mRS score at 90 days after stroke onset.
- (4) NIHSS score at 18–24 hours after procedure, 24–74 hours after procedure, and 5–7 days after stroke onset and their changes from baseline.
- (5) Proportions of patients with a NIHSS score = 0 or 1, a NIHSS score = 0–2, a NIHSS score improvement  $\geq 4$  points, and a NIHSS score improvement  $\geq 8$  points at 18–24 hours after procedure, 24–74 hours after procedure, and 5–7 days after stroke onset.
- (6) Glasgow coma scale score (GCS) at 18–24 hours after procedure, 24–74 hours after procedure, and 5–7 days after stroke onset and their changes from baseline.
- (7) Barthel Index score (BI) and proportions of patients with BI = 95–100 at 30 and 90 days after stroke onset.
- (8) EQ-5D-5L score at 90 days after stroke onset.
- (9) eTICI score and successful reperfusion rates before and after EVT.
- (10) mAOL score and recanalization rates at 24–72 hours after procedure.
- (11) PC-ASPECTS score at 24–72 hours after procedure and 5–7 days after stroke onset.
- (12) Lesion volume based on quantitative imaging detection at 24–72 hours after procedure and 5–7 days after stroke onset.

### 2.2 Safety endpoints

The safety endpoints include:

- (1) All-cause mortality within 7, 30, and 90 days after stroke onset.
- (2) Proportions of patients with intracranial hemorrhage and symptomatic intracranial hemorrhage at 24–72 hours after procedure and 5–7 days after stroke onset.
- (3) Proportions of patients with new regional cerebral embolisms during EVT.
- (4) Proportions of patients with new cerebral infarction at 24–72 hours after procedure and 5–7 days after stroke onset.
- (5) EVT procedure-related complications within 90 days after stroke onset.
- (6) Other serious adverse events within 90 days after stroke onset.

### 3. Statistical analysis

#### 3.1 Analysis datasets

##### 3.1.1 Intention-to-treat population (ITT)

The ITT population includes all randomized subjects, and the analysis will be conducted based on their randomized treatment groups according to the intention-to-treat principle.

##### 3.1.2 Modified intention-to-treat population (m-ITT)

The m-ITT population includes all randomized subjects who received either IVT followed by EVT or EVT alone treatment. The analysis will be conducted based on their randomized treatment groups following the intention-to-treat principle.

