If the efficacy advantage of the IVT followed by EVT group over the EVT alone group is less than anticipated, the sample size may be expanded appropriately, with an upper limit of no more than 20% of the original sample size. If the efficacy of the two groups appears to be similar, the study design will shift to a non-inferiority framework, evaluating whether EVT alone is non-inferior to IVT followed by EVT. Assuming similar efficacy (with both groups achieving a 90-day mRS score ≤ 2 in 42.03% of patients), the current sample size of 170 patients per group provides 80% power to test non-inferiority, with a one-sided type I error rate of 0.025 and a non-inferiority margin of -15% in rate difference. The interim analysis and sample size re-estimation will be conducted under the strict control of the DSMB to ensure that the type I error rate is not inflated.

The primary analysis of this study will follow the intention-to-treat (ITT) principle. The main analysis will be conducted on the modified intention-to-treat (m-ITT) population, defined as all randomized patients who received treatment, analyzed according to their original randomization group. Additional populations, such as the As-Treated Set (ATS) and the Per-Protocol Set (PPS), will be used for sensitivity analyses. Except for the primary efficacy endpoint, which will be tested using a one-sided significance level of 0.025 for superiority or non-inferiority evaluation, all other statistical tests will be conducted using a two-sided significance level. A P-value < 0.05 will be considered statistically significant for these comparisons.

1. Introduction and background

Stroke is a leading cause of death and disability in China, with acute ischemic stroke (AIS) accounting for approximately 85% of all acute strokes. Among these, large vessel occlusion-related AIS (AIS-LVO) represents about 20% of cases^[1]. Posterior circulation infarction, which occur in the vertebrobasilar artery territory, comprise 20–25% of all ischemic strokes. Although less common than anterior circulation ischemic strokes, posterior circulation infarctions—particularly AIS caused by basilar artery occlusion (AIS-BAO)—often present with severe symptoms and poor outcomes. Due to the heterogeneity of initial symptoms and diagnostic challenges, AIS-BAO frequently results in poor prognoses, posing significant challenges in clinical diagnosis and treatment.

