##### 3.1.3 As treated set (AT)

The AT population is defined the same as the m-ITT population but will be analyzed based on the actual treatment received.

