##### 3.1.4 Per-protocol set (PPS)

The PPS population includes subjects in the m-ITT population who did not experience any significant protocol deviations, as determined by the sponsor.

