##### 3.1.5 Safety analysis set (SS)

The SS population includes all subjects who received either IVT followed by EVT or EVT alone treatment and had at least one safety follow-up.

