### 3.9 Efficacy analysis

Efficacy analysis will be performed on the m-ITT, AT, and PPS datasets. The m-ITT dataset will be the primary analysis set for efficacy evaluation, while the AT and PPS datasets will serve as sensitivity analyses.

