### 3.10 Safety analysis

Safety analysis will be performed using the SS dataset.

All adverse events (AEs) reported during the clinical trial will be summarized. AEs will be coded using MedDRA and classified by SOC and PT. For incidence rate calculations, if a subject experiences multiple different AEs, they will be counted as one case for the overall incidence rate. If the same AE occurs multiple times in the same subject, the subject will still be counted as one case for the incidence calculation of that AE. For severity analysis, only the most severe occurrence of the same AE in a subject will be included. Additionally, if a subject experiences multiple AEs within the same SOC and PT, they will only be counted once for the incidence rate calculation within that SOC and PT.

The incidence, number of cases, and rate of all safety endpoints will be summarized. Exact Clopper-Pearson 95% CIs will be calculated for incidence rates. Group comparisons will use chi-square tests, continuity-corrected chi-square tests, or Fisher's exact test, as appropriate, with P-values reported. RD and RR with 95% CIs will also be calculated.

Mortality events will be analyzed using Kaplan-Meier methodology, with median survival time and 95% CIs reported. Kaplan-Meier survival curves will be plotted, and group comparisons will use the log-rank test with P-values reported.

A list of all AEs, serious AEs, adverse reactions, and serious adverse reactions (SS dataset) will be provided.

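### No planned efficacy analysis covers all randomised patients, and the SAP's treated-patient wording is narrower than the protocol's, so read literally it drops alteplase-only and EVT-then-IVT patients from the main and safety sets

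*SAP*

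**What the plan says.** **Principle.** The Protocol Summary (sample size and statistical methods) and Protocol 10.2 say that the primary analysis follows the intention-to-treat principle. Both then name a modified set as the main one, in the Summary "defined as all randomized patients who received treatment, analyzed according to their original randomization group". Protocol 10.2 refers to the SAP for population definitions.

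**Sets in SAP 3.1.**
- ITT: "The ITT population includes all randomized subjects".
- m-ITT: "The m-ITT population includes all randomized subjects who received either IVT followed by EVT or EVT alone treatment".
- As-treated: "The AT population is defined the same as the m-ITT population", regrouped by treatment actually received.
- Per-protocol: "The PPS population includes subjects in the m-ITT population" without significant deviations.
- Safety: "The SS population includes all subjects who received either IVT followed by EVT or EVT alone treatment and had at least one safety follow-up".

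**Use of the sets.** SAP 3.9: "Efficacy analysis will be performed on the m-ITT, AT, and PPS datasets". Subgroups (SAP 3.9.3) use m-ITT. SAP 3.10: "Safety analysis will be performed using the SS dataset". SAP 3.2.2 says that ITT is grouped as randomised and that the safety set is grouped by actual intervention. SAP 3.5 uses ITT for disposition, set membership, protocol deviations and listings.

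**Related definitions.** Protocol 5.1 starts EVT when the guiding catheter enters the sheath and counts earlier angiography as screening. Protocol 5.3 allows EVT-alone patients without successful reperfusion to receive intravenous rtPA afterwards, under conditions.

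**The concern.** There are two gaps of different strength.

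The first holds on any reading. A patient who is randomised and then receives neither IVT nor EVT is in the ITT set only, and no efficacy endpoint is analysed there. Treating teams know the allocation, so whether treatment is started can depend on the arm. No all-randomised result is planned against which to check the main one.

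The second depends on how the SAP phrase is read. Alteplase without EVT is literally neither of the two listed treatments, and nor is EVT followed by IVT. On that reading, membership of the main set and of the only safety comparison set depends on what happens after randomisation. Alteplase can itself cause some of those events, such as early reperfusion, bleeding or death before the catheter is in. EVT followed by IVT is selected on failed reperfusion. Excluding patients on such events can bias the comparison in either direction. Data collection is not at issue: deaths are reported as SAEs (Protocol 9.2.2) and the DSMB reviews all accumulated safety data (Protocol 9.4). What can be lost is inclusion in the planned between-group comparisons.

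**Working it through.** **1. Who is in which set**

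| Randomised patient | ITT | Protocol m-ITT | SAP m-ITT, literal | SAP safety set, literal |
|---|---|---|---|---|
| No IVT, no EVT | yes | no | no | no |
| Alteplase, no guiding catheter inserted | yes | yes | no | no |
| EVT, then IVT | yes | yes | no | no |
| EVT alone, or IVT then EVT | yes | yes | yes | yes, with a safety follow-up |

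The as-treated set has the m-ITT members and the per-protocol set is a subset, so neither restores a patient from the first three rows. If the SAP phrase only names the two strategies, rows two and three become yes. Row one does not change.

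**2. The plan's own figures**

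Inputs (Protocol 10.1): 42.03% and 26.14%, one-sided 0.025, power 80%, dropout 20%, margin 15 points.

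- Superiority, unpooled variance: (1.960 + 0.842)² × (0.4203×0.5797 + 0.2614×0.7386) / 0.1589² = 135.8, so 136 per group. Then 272 / 0.80 = 340.
- Non-inferiority power at 170 per group, 42.03% in both: 80.0%.

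The design figures reproduce. The point rests on set definitions, not on a sample-size error.

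**3. Illustrative shift in the rate difference**

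Let x and y be the shares excluded from the IVT and EVT-alone arms, and g and h the good-outcome rates among them. All four are assumptions, with g from 0 to 70% and h from 0 to 50%.

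Shift = [(0.4203 - x·g)/(1 - x) - (0.2614 - y·h)/(1 - y)] - 0.1589

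- x = y = 2%; g = 70%, h = 0: 0.4146 - 0.2667 - 0.1589 = -1.10 points.
- x = y = 2%; g = 0, h = 50%: 0.4289 - 0.2565 - 0.1589 = +1.34 points.
- x = 5%, y = 2%; g = 70%, h = 0: 0.4056 - 0.2667 - 0.1589 = -2.01 points.
- x = 5%, y = 2%; g = 0, h = 50%: 0.4424 - 0.2565 - 0.1589 = +2.70 points.
- g = 42.03%, h = 26.14%: zero for any x and y.

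**4. What a one-arm exclusion does to error rates**

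Assume that 5% of the IVT arm only is excluded (8.5 of 170), with no other loss, normal approximation and unpooled variance. Non-inferiority means EVT alone against IVT followed by EVT.

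- No good outcomes among the excluded: one-sided superiority error rises from 2.5% to 4.7% (both arms 26.14%) or 6.0% (both 42.03%). Non-inferiority power is 65.2%, against 79.0% if the same number excluded match their arm.
- 80% good outcomes among the excluded: superiority power is 77.4%, against 87.1% if they match. The chance of declaring non-inferiority at a true 15-point deficit (42.03% against 27.03%) rises from 2.5% to 5.8%.

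**5. Safety, per patient**

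Take an assumed group of 170 and an assumed event rate r. One excluded patient with an event shifts the rate by (170r - 1)/169 - r: -0.56 points at r = 5% and -0.36 at r = 40%. One excluded patient without an event shifts it by 170r/169 - r: +0.03 and +0.24. The real denominators are unknown, because the safety set is grouped by actual intervention and the SAP names no group for an alteplase-only patient.

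**The case against.** The strongest reply is that both documents openly prespecify m-ITT as the main set, and that the SAP phrase simply names the two strategies, as the intervention sections do. The literal reading would expel EVT-alone patients who receive IVT afterwards, which Protocol 5.3 permits. It is unlikely that the authors meant that. This stands as an argument about intent. It does not settle the text, because the SAP is where the protocol sends the reader for definitions and its words are narrower.

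SAP 3.2.2 mentions ITT among the analysed sets. That is a grouping rule and assigns no endpoint.

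The group exposed to the literal reading is also limited. A patient found reperfused once the guiding catheter is in the sheath has started EVT under Protocol 5.1 and stays in.

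A reader might infer four stronger points, which the documents do not support:

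- **That ITT must replace m-ITT as primary.** The choice is stated openly, so replacing it is debatable.
- **That the rule against exclusion after allocation is revealed (Protocol 8.2, SAP 1.6) is broken.** That rule concerns taking part in the study, not analysis sets.
- **That early deaths are lost through the follow-up condition.** Protocol 9.3.1 treats death as an end of follow-up, and the visit schedule records death, ICH and AE/SAE from the treatment column on. What remains is a missing detail.
- **That the wording hides alteplase harm.** Omitted events lower a rate and omitted event-free patients raise it, so no direction can be claimed.

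**Conclusion.** The point holds in two parts. It is certain from the text that no efficacy analysis is planned on all randomised patients, and that the SAP's membership wording is narrower than the protocol's. Whether alteplase-only and EVT-then-IVT patients would actually be left out depends on a reading that the documents leave open, so the passages must be reconciled.

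The size is unknown. The documents give no rate of untreated, alteplase-only or EVT-then-IVT patients and no outcomes for them. The range of -2.01 to +2.70 points pairs opposite extremes across the arms and does not separate untreated from alteplase-only patients. The error rates in step 4 assume exclusion from one arm only, whereas the literal reading can touch both. All of these figures are illustrations, and the bias is zero if excluded patients do as well as their arm. The gap should be fixed because the remedy is cheap and closes a possible post-randomisation exclusion. Nothing here shows that the result will be biased.

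**What to change.** - Keep m-ITT as the stated main set. Add to SAP 3.9 a prespecified analysis of the primary endpoint on all randomised patients, as randomised.
- Define m-ITT as randomised patients in whom any IVT or EVT was started.
- Define the safety set as all patients in whom any IVT or EVT was started. State the as-treated group for alteplase-only and for EVT-then-IVT patients, and say that a recorded death or adverse event counts as safety follow-up.
- Use the same wording in Protocol 10.2 and SAP 3.1.

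**Cost.** One extra analysis, and an amendment reported to the ethics committee (Protocol 13.3). Untreated patients slightly dilute the contrast. This matters more under non-inferiority, so m-ITT and per-protocol results should stay beside the new one. If the SAP 3.2.3 rule is extended to all randomised patients, those with unknown survival are scored mRS 6. For each 1% of an arm scored this way who would otherwise match the arm average, the rate falls by 0.01 × 42.03 = 0.42 points (IVT followed by EVT) or 0.01 × 26.14 = 0.26 points (EVT alone).
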